	
V16 (Week 216) for the post-treatment observation visit.
 
Note: At the end of the 52-week blinded treatment period, all patients will be evaluated for safety and efficacy, and for eligibility to transition to the LTFU period and receive GZ/SAR402671.
 
Note: For patients transitioning to a long-term study with GZ/SAR402671, Week 208 (V15) will be the last study visit.
 
Using Day 1 as reference, a time frame of ± 3 days is acceptable from Visit 4 to 8 of Part 2 study visits, and ± 14 days for Visit 9 and 16. (If one visit date is skipped/missed/changed, the next visit should take place according to the original schedule).
 
Patients will be followed in the LTFU period for 36 months (156 weeks).
 
Note: All patients who prematurely discontinue study medication prior to Week 8 (Visit 8) in Part 1, or Week 52 (Visit 9) in Period 2 or Week 208 (Visit 15) in Period 3 of Part 2 will be asked to continue study visits for safety and efficacy assessments up to and including the last scheduled visit. At a minimum, the patient should be followed up for at least 8 weeks after their last scheduled received dose. Patients who prematurely and permanently discontinue study medication should complete an end of treatment assessment visit (similar to Week 8/Visit 8 in Part 1 or Week 52/Visit 9 in Part 2 [for either Period 2 or 3]) followed by a 8-week post-treatment follow-up visit (similar to Visit 9 in Part 1 or Visit 16 in Part 2 [for either Period 2 or 3]). If the following examinations including lumbar puncture, DAT scan, and PK analyses on plasma and CSF have been performed recently, then the Investigator can discuss with Sponsor the need to repeat these examinations. Repeat examination(s) will be done on a patient by patient basis.

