Visit number	9.1 (for Japanese patients only)	10	10.1 (for Japanese patients only)	11	11.1 (for Japanese patients only)	12	12.1 (for Japanese patients only)	13	13.1 (for Japanese patients only)	14	14.1 (for Japanese patients only)	15	16
MDS-UPDRS (including H&Y)		X		X		X		X		X		X	X
PD-CRS		X		X		X		X		X		X	
MoCA		X		X		X		X		X		X	
SDMT (oral)		X		X		X		X		X		X	
TMT-A; TMT-B		X		X		X		X		X		X	
BDI-II		X		X		X		X		X		X	X
PDQ-39		X		X		X		X		X		X	
EQ-5D		X		X		X		X		X		X	
FES		X		X		X		X		X		X	
HRPQ		X		X		X		X		X		X	

Abbreviations: AE, adverse event; BDI-II: Beck Depression Inventory, second edition; CGI: Clinical Global Impression; DAT: dopamine transporters; DAT scan, ioflupane I-123 injection DaTSCAN; ECG: electrocardiogram; EQ-5D: EuroQol Five Dimensions questionnaire; FES: Falls Efficacy Scale; GL-1: glucosylceramide; H&Y: Hoehn and Yahr; HRPQ: Health-Related Productivity questionnaire; IMP, investigational medicinal product; lyso-GL-1: glucosylsphingosine; MDS-UPDRS: Movement Disorder Society-Unified Parkinson's Disease Rating Scale; MoCA: Montreal Cognitive Assessment; PD: Parkinson's disease; PD-CRS: Parkinson's Disease-Cognitive Rating Scale; PDQ-39: Parkinson's Disease Questionnaire – 39; qd, daily; SDMT: Symbol Digit Modalities Test; TMT-A: Trail-Making Test A; TMT-B: Trail Making Test B; WOCBP: women of childbearing potential.

- a* This is the study completion visit, and it should be done 8 weeks after last IMP dose; this visit also applies to early withdrawal or treatment discontinuation, if applicable. This does not apply to patients who will transition to a long-term study with GZ/SAR402671 (last visit will be week 208).
- b* Retrieve patient diary. For patients transitioning to a long-term study with GZ/SAR402671 the patient diary will be retrieved at week 208.
- c* Plasma biomarkers, including plasma GL-1 and lyso-GL-1.
- d* After 52 weeks, the patient is required to have a full ophthalmological examination at Weeks 104, 156, 208, and early withdrawal or treatment discontinuation, if applicable. Visual acuity check, slit lamp examination and funduscopy without pupil dilation are only required at Weeks 78, 130, 182, and 216 (at the 8-week follow-up [Period 4] visit). Pupil dilation/full evaluation can be performed at any time if deemed medically necessary.

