- e* For patients already on PD medications at the time of randomization, all efficacy assessments must be done in the patient's "OFF" state (no PD medication may be taken for at least 12 hours prior to the first efficacy assessment).
- f* Visit window extended up to 3 months, during Covid-19 outbreak ([Section 10.1.2](#)).

Note: Visits in Weeks 65, 91, 117, 143, 169, and 195 are for Japanese patients only.

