10.1.2 Part 2: Treatment phase

In Part 2, the GZ/SAR402671 dose will be the highest dose determined to be safe and well tolerated in Part 1. If patients from Part 1 continue to meet eligibility requirements, they may enroll in Part 2, but rerandomization will be required. All assessment at baseline will need to be repeated, except for the genetic screening, MRI, LP, and DAT scan, to confirm eligibility of patients from Part 1 to enroll in Part 2 (see study flowchart, [Section 1.3.2](#)).

Visit window: The randomization visit (Day 1) can be performed within 60 days from the screening visit. For Week 2 through Week 39 visits, a time frame of ± 3 days is acceptable using Day 1 as reference. For Week 52, a visit window of ± 14 days is acceptable using Day 1 as a reference. After Week 52 and throughout Period 3, a visit window of ± 7 days for all visits is acceptable using Day 1 as reference. For Week 216, a visit window of ± 14 days is acceptable using Day 1 as a reference. (If one visit date is skipped/missed/changed, the next visit should take place according to the original schedule).

Covid-19 outbreak

Due to Covid-19 outbreak, on-site visits may be delayed with visit window extended up to 3 months. In this case, IMP can be dispensed to the patient (via direct-to-patient) for a maximum duration of 6 months without on-site visit, but with a follow-up by phone (see [Section 10.1.2.12](#)). If Week 52 visit is delayed, the blinded treatment will be continued until Week 52 visit is performed and eligibility assessed for LTFU period.

Prior to dispensing the IMP, the Investigator will contact (phone, on-line) the patient to review AE/SAE/concomitant medication to ensure that no safety issues contraindicate the prolongation of the IMP. During the time of IMP prolongation, the Investigator will make every effort to contact the patient every 2 weeks to assess the safety. All examinations required for safety that can't be done at the site can be performed locally at a minimum laboratory assessment.

The on-site visit should be scheduled as close as possible to the theoretical visit date, particularly Week 52 which is mandatory.

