10.1.2.10 Long term follow-up period (Period 3)

Patients who complete the 52 weeks of double-blinded treatment and who continue to meet inclusion criteria [I 06](#), [I 07](#), [I 08](#), and [I 09](#) and none of the exclusion criteria (exclusion criteria [E 02](#), [E 03](#), [E 05](#), and [E 06](#) will not need to be rechecked) will be eligible to enroll to the LTFU period (Period 3) where they will continue to receive appropriate monitoring and will receive GZ/SAR402671 treatment after Visit 9. It is important to note that patients will not be informed of when the switch will occur, nor will the person(s) performing any of the evaluations.

Throughout Period 3, a visit window of ± 7 days for all visits is acceptable using Day 1 as reference.

During this period, a clinic visit will be scheduled at 6-month intervals (Weeks 78, 104, 130, 156, 182, and 208) and patients will receive GZ/SAR402671, orally, at the clinic. For Japanese patients only, additional clinic visit will be scheduled at Weeks 65, 91, 117, 143, 169, and 195 (Visits 9.1, 10.1, 11.1, 12.1, 13.1, and 14.1) in addition to the above 6-month interval visits.

Before dosing, the following assessments will be performed at each study visit (every 6 months), as listed in the study flow chart, [Section 1.3.3](#), which should be done in the following order:

- Whenever possible, the following scales and questionnaires should be done prior to clinical interaction with the Investigator:
 - BDI-II ([Appendix L](#))
 - PDQ-39 ([Appendix O](#))
 - EQ-5D ([Appendix P](#))
 - HRPQ ([Appendix R](#))
 - FES ([Appendix Q](#))
- MDS-UPDRS, including H&Y ([Appendix F](#))
- PD-CRS ([Appendix G](#))
- Other questionnaires and scales
 - MoCA ([Appendix I](#))

- Oral SDMT ([Appendix J](#))
- TMT-A; TMT-B ([Appendix K](#))
- Review of concomitant medications (every 3 months [13 weeks] for Japanese patients only)
- General neurological examination
- Visual acuity check, slit lamp examination, and fundoscopy without pupil dilation at Visits 10, 12, and 14; at Visits 11, 13, and 15, patients will have a full ophthalmology examination and photography (must be performed after the neurological examination)
- Vital signs: systolic and diastolic blood pressure (mm Hg), heart rate (bpm), respiratory rate (breaths/minute), and temperature (°C) (every 3 months [13 weeks] for Japanese patients only)
- Urine pregnancy test (for WOCBP)

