- Review of current medical conditions, with AE/SAE reporting (if any) (every 3 months [13 weeks] for Japanese patients only)
- Dispense IMP

At Visit 11/Week 104, Visit 13/Week 156, and Visit 15/Week 208 (ie, yearly), the following additional assessments will be performed, as listed in the study flow chart, [Section 1.3.3](#):

- Blood sampling for biomarker analysis
- Physical examination and record of body weight measurement
- 12-lead ECG
- Laboratory assessments (to be performed by the central laboratory):
 - Hematology: CBC, with differential and platelet count; coagulation profile: PT, PTT, and INR
 - Biochemistry: Sodium, potassium, chloride, calcium, ALT, AST, GGT, ALP, total and conjugated bilirubin, urea, serum creatinine, glucose, albumin, total proteins
- Urinalysis (dipstick) including glucose, protein, bilirubin, urobilinogen, pH, specific gravity, blood, ketones, nitrite, and leucocytes. Central urinalysis will be performed if any abnormality is observed in the urinalysis dipstick test.
- DAT scan
- Dispense IMP (except Visit 15/Week 208)
- Retrieve patient diary (at Visit 15/Week 208, only for patients who will transition to a long-term study with GZ/SAR402671).

Remind patient to return to the clinic for next visit.

Remind patient to not take the dose at home on the clinic visiting day, the IMP will be taken at clinic.

At Visit 15 (Week 208), patients will receive their last dose of GZ/SAR402671 at the clinic.

Visit 15 (Week 208) will be the last study visit for patients who will transition to a long-term study with GZ/SAR402671.

10.1.2.11 Eight-week follow-up visit (Period 4, end-of-study visit, Visit 16: Week 216 ±14 days)

This will be the last study visit. Patients who prematurely and permanently discontinue study medication should complete an end of treatment assessment visit (similar to Week 52/end of treatment visit for Period 2, Part 2) followed by a 8-week post-treatment follow-up visit (Visit 16). The following assessments will be performed as listed in the study flow chart, [Section 1.3.3](#), which should be done in the following order:

- BDI-II (Appendix L)
- MDS-UPDRS, including H&Y ([Appendix F](#))
- Review of concomitant medications
- Physical examination
- General neurological examination
- Visual acuity check, slit lamp examination, and fundoscopy without pupil dilation
- Vital signs: systolic and diastolic blood pressure (mm Hg), heart rate (bpm), respiratory rate (breaths/minute), and temperature (°C)

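### Visit 16 is timed both from Day 1 and from the last dose, so the drug-free interval it measures can run from 5 to 11 weeks instead of 8

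*Protocol*

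**What the plan says.** Four places in the protocol govern when Visit 16 happens.

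- **From Day 1.** Section 10.1.2 states "For Week 216, a visit window of ± 14 days is acceptable using Day 1 as a reference". The Assessment schedule in the Clinical Trial Summary likewise counts from Day 1 and lets Visits 9 and 16 fall up to 14 days either side. The heading of section 10.1.2.11 repeats Week 216 ±14 days.
- **From the last dose.** Section 1.3.3, footnote a: "This is the study completion visit, and it should be done 8 weeks after last IMP dose". The footnote also applies the visit to early withdrawal and treatment discontinuation.

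Three further rules decide how far apart these two timings can fall.

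- The last dose belongs to the preceding visit (section 10.1.2.10): "At Visit 15 (Week 208), patients will receive their last dose of GZ/SAR402671 at the clinic". That visit has its own window: "Throughout Period 3, a visit window of ± 7 days for all visits is acceptable using Day 1 as reference".
- When a visit moves, section 10.1.2 says: "If one visit date is skipped/missed/changed, the next visit should take place according to the original schedule".
- Under the Covid-19 provisions of section 10.1.2, "on-site visits may be delayed with visit window extended up to 3 months". Section 1.3.3 attaches the same extension to Week 208 through footnote f.

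No text says which reference point prevails when Visit 15 is not exactly at Week 208.

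**The concern.** The purpose of Visit 16 is to observe patients off drug. Amendment 06 lengthened the gap before it and added MDS-UPDRS and BDI-II so that the course after stopping would be better recorded. For such an observation, the clock that matters starts at the last dose. A window counted from Day 1 does not fix that interval, because Visit 15 can itself move by a week either way. The rule that the next visit keeps its original date makes this worse: a late Visit 15 shortens the interval and an early one lengthens it.

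Two things are at stake. The off-drug scores would come from patients at quite different times since stopping, some of them still on treatment by the protocol's own definition. Sites also cannot tell which date is compliant when the two rules disagree.

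**Working it through.** **Inputs**

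- Visit 15 (last dose): Week 208, ±7 days from Day 1 (sections 10.1.2 and 10.1.2.10).
- Visit 16: Week 216, ±14 days from Day 1 (section 10.1.2; Clinical Trial Summary).
- Alternative timing of Visit 16: 8 weeks after last dose (section 1.3.3, footnote a).
- On-treatment period: up to 6 weeks, or 42 days, after last dose (sections 9.3 and 11.4.3).

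**1. Nominal interval.** Visit 15 is at 208 × 7 = 1456 days and Visit 16 at 216 × 7 = 1512 days. The difference is 56 days, which reproduces the stated 8 weeks.

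**2. Range when both visits are inside their Day 1 windows.**

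- Shortest: (1512 − 14) − (1456 + 7) = 1498 − 1463 = 35 days (5 weeks).
- Longest: (1512 + 14) − (1456 − 7) = 1526 − 1449 = 77 days (11 weeks).

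The longest interval is 77/35 = 2.2 times the shortest. At 35 days the visit falls 7 days inside the 42-day on-treatment period.

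**3. Range if Visit 16 is timed from the actual last dose, ±14 days.** 56 − 14 = 42 days to 56 + 14 = 70 days (6 to 10 weeks), whatever the date of Visit 15. The earliest permitted day is then the last day of the on-treatment period.

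**4. Effect of a delayed Visit 15.** Let Visit 15 be d days late and Visit 16 stay on its Day 1 schedule (days 1498 to 1526, Weeks 214 to 218). The interval then runs from 1498 − (1456 + d) = 42 − d to 1526 − (1456 + d) = 70 − d.

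| Delay of Visit 15 | Interval to Visit 16 |
|---|---|
| 28 days | 14 to 42 days |
| over 42 days | early edge of the window precedes the last dose |
| over 70 days | whole window precedes the last dose |
| 91 days (about 3 months) | −49 to −21 days |

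Section 10.1.2 gives rules for a delayed Week 39 that overlaps Week 52 and a delayed Week 52 that overlaps Week 65. It gives none for Weeks 208 and 216.

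**5. Like-for-like comparison with the superseded visit.** The amendment summary gives the replaced visit as Week 214 ±1 week. With the same Visit 15 window, the range was (214 × 7 − 7) − 1463 = 28 days to (214 × 7 + 7) − 1449 = 56 days.

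**The case against.** The strongest reply is that this is a small inconsistency in a visit that carries little weight. The listed exploratory endpoints and the second analysis step in section 11.5.2 stop at Week 208. Patients who move to the long-term study end at Visit 15. The ±14-day width is deliberate: Amendment 06 says that more flexibility on the window was wanted. With the half-life of 31.3 hours quoted in section 4.2.1, even 35 days (840 hours) is about 27 half-lives. All of this stands and limits the importance of the point. It does not remove the conflict. The fault is the reference point and not the width, and the half-life speaks to drug exposure but not to how symptoms evolve after stopping.

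A reader might infer three stronger things that the protocol does not support.

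- **That Visit 16 can routinely be scheduled before the last dose.** For the whole window to precede the last dose, three things are needed: a Covid-19 delay of Visit 15 beyond 70 days, dosing continued to that visit, and no matching delay of Visit 16. The Covid-19 text covers on-site visits in general and does not exclude Visit 16. It provides explicitly for continued treatment up to a delayed visit only for Week 52. Period 4 is described throughout as post-treatment.
- **That the amendment shortened the wash-out.** Setting 35 days against the former nominal 6 weeks compares a minimum with a nominal value. Like for like, the range moved from 28–56 to 35–77 days, so both ends are later.
- **That a stated 8-week minimum follow-up is breached for completers.** That minimum is written for patients who discontinue early (Clinical Trial Summary; section 10.3.4) or whose blind is broken (section 8.3.2). For completers the text at odds with the Day 1 window is footnote a.

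**Conclusion.** The protocol gives Visit 16 two unreconciled reference points. Under the Day 1 rule, a completer whose visits are both in window can be seen 35 to 77 days after the last dose instead of 56, and at the short end is still in the on-treatment period. This rests only on the ordinary windows and on the last dose being taken at Visit 15. A Covid-19 delay of Week 208 shortens the interval further if Visit 16 is held to its original date.

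The consequence is confined to the interpretability of the off-drug MDS-UPDRS and BDI-II scores and to site compliance. The Week 52 primary and secondary analyses are untouched. The correction is still worth making, because the reading at stake is the one Amendment 06 was written to obtain.

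**What to change.** The sponsor should reconcile the Clinical Trial Summary (Assessment schedule), section 1.3.3 footnote a, section 10.1.2 and the heading of section 10.1.2.11 to one reference point for Visit 16. The option that fits the amendment's purpose is 8 weeks ±14 days from the actual last dose:

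- Remove the Day 1 reference for Visit 16 from the Clinical Trial Summary and section 10.1.2.
- State the ±14 days in footnote a, and align the 10.1.2.11 heading with it.
- Exempt Visit 16 from the sentence that keeps the next visit on its original date, in both the Clinical Trial Summary and section 10.1.2. Otherwise the conflict survives the edit.

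This holds the in-window interval to 42 to 70 days, and the window can no longer open before the last dose. It also matches what early discontinuers already need, since a Week 216 date counted from Day 1 cannot mean 8 weeks after their last dose.

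Wherever Visit 16 MDS-UPDRS and BDI-II are reported, give the actual days since last dose alongside.

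The cost is wording in a few places and no additional visit. For some patients the date of Visit 16 will move with Visit 15.

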10.1.2.1 Visit 1: Screening from Day -60 to -1 (Period 1)

The following activities will be performed:

- An explanation of the purpose, procedures, potential risks and benefits of this study will be provided to the patient.
- Informed consent signature and date will be collected.
- In addition to recording any safety issue, the patient diary will also be used to record any missing doses after randomization. The patient should bring their diary and any remaining capsules to each clinic visit. The site staff will review the patient diary during each clinic visit and record excursions from treatment into the eCRF. The patient diary will be retrieved when the patient finishes their participation in the study.
- One blood sample will be collected for investigation of GBA mutations required to include patients in the study (see [Section 9.6](#)). See [Section 17 \(Appendix A\)](#) for a list of GBA mutations. This gene will be sequenced even if historical results are available. Also, this sample will be investigated for a specific mutation in the LRRK2 gene (G2019S) and patients carrying this mutation will be excluded. **Of note, if patient meets these two criteria, then the screening visit may proceed for all other items described below.**
- Patient demography will be recorded.
- BDI-II ([Appendix L](#)): At screening, patients with BDI-II of 20-28, inclusive, should be evaluated by a mental health specialist before the Investigator can determine if the patient would be able to fully participate in the trial. Patients with a BDI-II of >28 (severe depression) at screening will be excluded.
- Confirmation of eligibility by the Investigator
- GBA complete gene sequencing and LRRK2 G2019S genotyping
- Medical/surgical history and PD history
- Confirmation of diagnosis of RBD (historically documented polysomnography or RBD screening questionnaire)
- Review of prior medications
- Physical examination
- General neurological examination
- Record of height and body weight measurements
- Vital signs (orthostatic): systolic and diastolic blood pressure (mm Hg), heart rate (bpm), respiratory rate (breaths/minute), and temperature (°C)
- 12-lead ECG
- Laboratory assessments (to be performed by the central laboratory):

- Hematology: CBC, with differential and platelet count; coagulation profile: PT, PTT, and INR
- Biochemistry: Sodium, potassium, chloride, calcium, ALT, AST, GGT, ALP, total and conjugated bilirubin, urea, serum creatinine, glucose, albumin, total proteins
- Urinalysis (dipstick) including glucose, protein, bilirubin, urobilinogen, pH, specific gravity, blood, ketones, nitrite, and leucocytes. Central urinalysis will be performed if any abnormality is observed in the urinalysis dipstick test.
- Serum β -HCG pregnancy test (for WOCBP)
- Full ophthalmology examination and photography
- Review of current medical conditions, with AE/SAE reporting (if any)
- GCase activity: dried blood spot from whole blood sample for genetic testing
- MDS-UPDRS ([Appendix F](#))
- Hoehn and Yahr ([Appendix F](#)); for patients on a stable dose of PD medication, this should be done in the “ON” state.
- PD-CRS ([Appendix G](#))
- MoCA ([Appendix I](#))

If patients demonstrate eligibility based on all previous screening criteria:

- MRI (without contrast) scan will be performed (at least 7 days prior to the end of the screening period [Day -8]).
- LP for collection of CSF will be performed (within 14 days prior to randomization or at Day 1, pre-dose).
- DAT scan will be performed (within 7 days prior to randomization or at Day, 1 pre-dose).

10.1.2.2 Visit 2: Randomization/baseline at Week 0/Day 1

Baseline assessments will be completed within the 60-day screening period. Eligibility will be reconfirmed prior to randomization/first dose administration on Day 1.

Patients will receive either placebo or GZ/SAR402671, orally, at the clinic.

The baseline visit (Day 1) will include assessments and activities as listed in the study flow chart, [Section 1.3.2](#), which must be done in the following order:

- Whenever possible, the following scales and questionnaires should be done prior to clinical interaction with the Investigator:
 - BDI-II ([Appendix L](#))
 - PDQ-39 ([Appendix O](#))
 - EQ-5D ([Appendix P](#))

- HRPQ ([Appendix R](#))
- CGI ([Appendix M](#))
- FES ([Appendix Q](#))
- Reconfirmation of eligibility by the Investigator
- Review of concomitant medications
- Randomization via IVRS
- MDS-UPDRS, including H&Y ([Appendix F](#))
- PD-CRS ([Appendix G](#))
- Other questionnaires and scales:
 - MoCA ([Appendix I](#))
 - Oral SDMT ([Appendix J](#))
 - TMT-A; TMT-B ([Appendix K](#))
- Physical examination
- General neurological examination
- Archival blood sample collected prior to the start of IMP
- Vital signs: systolic and diastolic blood pressure (mm Hg), heart rate (bpm), respiratory rate (breaths/minute), and temperature (°C)
- Laboratory assessments (to be performed by the central laboratory):
 - Hematology: CBC, with differential and platelet count; coagulation profile: PT, PTT, and INR
 - Biochemistry: Sodium, potassium, chloride, calcium, ALT, AST, GGT, ALP, total and conjugated bilirubin, urea, serum creatinine, glucose, albumin, total proteins
- Urinalysis (dipstick) including glucose, protein, bilirubin, urobilinogen, pH, specific gravity, blood, ketones, nitrite, and leucocytes. Central urinalysis will be performed if any abnormality is observed in the urinalysis dipstick test.
- Urine pregnancy test (for WOCBP)
- Review of current medical conditions, with AE/SAE reporting (if any)
- Blood sampling for biomarker analysis
- Blood sampling for PK analysis at multiple time points: at pre-dose and at 1, 2, 4, and 8 hours after IMP intake
- Pharmacogenetics DNA sample (optional; not applicable in Israel [[Appendix T](#)])
- DAT scan (only if not performed during the screening period, pre-dose)
- Lumbar puncture for collection of CSF (if not already done during the screening period) for biomarker and PK analyses

- Dispense IMP

Remind patient to return to the clinic for next visit, bring their diary and any remaining capsules.

Remind patient to not take the dose at home on the clinic visiting day, the IMP will be taken at clinic.

10.1.2.3 Visit 3: Week 0/Day 2

The following assessments should be done before dosing:

- Review of concomitant medications
- Vital signs: systolic and diastolic blood pressure (mm Hg), heart rate (bpm), respiratory rate (breaths/minute), and temperature (°C)
- Review of current medical conditions, with AE/SAE reporting (if any)
- Blood sampling for PK analysis (24 hours post-Day 1 dose PK sample or 1 hour before dosing)

Remind patient to return to the clinic for next visit, bring their diary and any remaining capsules.

Remind patient to not take the dose at home on the clinic visiting day, the IMP will be taken at clinic.

